### **3 STUDY IMPLEMENTATION**

#### **3.1 STUDY DESIGN**

This is a prospective, single institution, single arm, multi-cohort phase II study of sunitinib in subjects with recurrent gliosarcoma and primary CNS sarcoma that have failed prior surgery and irradiation (unless radiation therapy was contraindicated). Subjects will be classified into three cohorts: 1) Primary gliosarcoma; 2) Secondary gliosarcoma; 3) Primary CNS sarcoma. Cohort expansion will be carried out at indication of promising response.

##### **3.1.1 Optional Assessment of Free-Living Physical Activity and Sleep Quality**

Free-living physical activity and sleep quality will be quantified continuously using a small, non-invasive, portable watch accelerometer (Actigraph Inc., Pensacola FL) at the subject's wrist. Overall physical activity levels, daily changes, sleep duration and efficiency, amount of time spent in sedentary, moderate, vigorous intensity categories and estimated activity-associated energy expenditures will be extracted using established predictive equations.

Patients will be asked to wear the Actigraph device for Cycle 1 through Cycle 6. The patient will bring the Actigraph device to each patient visit to have the battery changed. This can be done in person at each visit, or via mail. Any lapses in Actigraph monitoring due to removal of the device by the patient, dead battery, or any unforeseen situations will not constitute a protocol deviation.

###### **3.1.1.1 Safety Considerations**

*Accelerometers.* These small watch-like monitors may cause slight discomfort to subjects. No other known risks are associated.

##### **3.1.2 Dose Limiting Toxicity (DLT)**

Toxicities will be graded according to the Common Terminology Criteria for Adverse Events (CTCAE) Version 5.0. Toxicities that occur during Cycle 1 will be evaluated for determination of DLT.

### **3.2 DRUG ADMINISTRATION**

Sunitinib 50 mg will be self-administered orally, once daily on an outpatient basis. Sunitinib will be administered at a dose of 50 mg daily for 2 consecutive weeks followed by 1 week of rest. Studies in patients with metastatic renal cell carcinoma, sunitinib tolerability was superior with the 2-weeks on and 1-week off compared to 4-weeks on and 2-weeks off.[\[13, 14\]](#) Patients should be instructed to store sunitinib at room temperature. Patient will take sunitinib once daily, with or without food, as desired. Patients should drink plenty of water or take rehydration fluids to avoid dehydration if diarrhea occurs. Patients should be alerted to the possibility that sunitinib capsules can cause a yellow discoloration of the skin on direct contact. If this happens, the patient should wash immediately with soap and water. Thyroid function will be monitored at baseline and at every two cycles. Dose reductions (to 37.5 mg and then 25 mg) will be permitted for patients experiencing grade 3 or 4 sunitinib-related toxicities.

**Abbreviated Title:** Ph II Sunitinib CNS Sarcomas

**Version Date:** 05-30-18

Because hypertension is a known and potentially serious but rare adverse event associated with sunitinib treatment, patients will have their blood pressure monitored and recorded at baseline and weekly during treatment including the weeks off the investigational drug either at the doctors' office or using any calibrated electronic device.

All subjects will be evaluated with magnetic resonance imaging at baseline and after every 2 cycles of treatment. Patients will continue treatment until there is disease progression or development of intolerable side effects.

### 3.3 DOSE MODIFICATIONS

Dose reductions (to 37.5 mg and then 25 mg) will be permitted for patients experiencing grade 3 or 4 sunitinib-related toxicities. If treatment is delayed for more than 4 weeks due to treatment associated toxicity, the patient will be discontinued from treatment and followed until disease progression.

- Patients may continue to receive therapy provided the following criteria are met on day 1 of each cycle:
  - ANC  $\geq 1.0 \times 10^9/L$
  - Platelets  $\geq 75 \times 10^9/L$
  - Non-hematological toxicity recovered to < grade 2 (or tolerable grade 2 or baseline)
  - No evidence of progressive disease
- With development of adverse events possibly related to sunitinib, dose reduction is permitted (see guideline below). If an adverse event is not covered by the guideline, dose may be reduced or held at the discretion of the investigator for the subject's safety. Subjects with adverse events that are manageable with supportive therapy may not require dose reductions (e.g. nausea/vomiting may be treated with antiemetics, diarrhea may be treated with loperamide, and electrolyte abnormalities may be corrected with supplements rather than by dose reduction).
- If a patient takes 75% or more of scheduled doses during a cycle, missed doses will not be reported as deviations. If the study team instructs a patient to hold the investigational drug, it will not be considered a protocol deviation.
- Increase in BP has been reported with use of anti-VEGF agents. Guidelines for management [15] is provided in Appendix 13.5

#### 3.3.1 Dose Modification Guidelines for Sunitinib Associated-Toxicity

Event	AE Grade or Observation	Dose Modification
Neutropenia	Grades 1 and Grade 2 $\geq 1200$	Maintain dose

**Abbreviated Title:** Ph II Sunitinib CNS Sarcomas

**Version Date:** 05-30-18

Event	AE Grade or Observation	Dose Modification
	Grade 2 < 1200 and Grade 3	Hold sunitinib until ANC $\geq$ 1,000, then reduce 1 dose level and resume treatment
	Grade 4	Hold sunitinib until ANC $\geq$ 1,000, then reduce 1 dose level and resume treatment
Thrombocytopenia	Grade 1	Maintain dose
	Grades 2-4	Hold sunitinib until platelets $\geq$ 75,000, then reduce 1 dose level and resume treatment
Fever or flu-like symptoms	Grades 1-4	Maintain dose
Fatigue	Grades 1 and 2	Maintain dose
	Grade 3 (and severe Grade 2, at investigator discretion)	Hold sunitinib until $\leq$ Grade 2, then reduce 1 dose level and resume treatment
QTc prolongation Do not use CTCAE grades	> 450 but $<$ 550 msec	Review patient's concomitant medications for QT interval-prolonging agents. Correct any electrolyte abnormalities. Continue sunitinib at current dose level.
	$\geq$ 550 msec	Stop sunitinib and any other QT-interval prolonging agents immediately. Correct any electrolyte abnormalities, then:  If there is a plausible explanation for AE other than sunitinib treatment and the contributing factor is removed, resume sunitinib at current dose level after the QTc returns to $<$ 550 msec.  If sunitinib may have contributed to the AE: Reduce 2 dose levels and restart sunitinib.  If QTc remains $<$ 500 msec after 14 days at reduced dose, increase one dose level and continue sunitinib.
Hand-foot syndrome	Grades 1 and 2	Maintain dose
	Grade 3	Hold sunitinib until $\leq$ grade 1, then resume treatment at same dose or reduce 1 dose level, at the discretion of the physician.
	Grades 1 and 2	Maintain dose

Event	AE Grade or Observation	Dose Modification
AST and/or ALT elevation	Grades 3 and 4	
Sunitinib should be dose delayed if elevation of ALT is <math>>5</math> x ULN, AST is <math>>5</math> x ULN, and/or bilirubin is <math>>3</math> x ULN.
 
Sunitinib may be re-administered when levels of ALT and AST are <math>\leq 5</math> x ULN and bilirubin is <math>\leq 3</math> x ULN. Sunitinib should not be re-administered if subjects develop <math>\geq</math> grade 3 hepatic failure (CTCAEv5 definition).
 
Patients must have LFTs checked at baseline and during each treatment cycle. LFTs should be obtained at any time when they are clinically indicated.

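### For an ANC of 1,000–1,199 and for severe Grade 2 fatigue, the hold in the dose-modification table is released by the same observation that triggers it

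*Combined protocol and SAP*

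**What the plan says.** **Neutropenia, Section 3.3.1.** The dose is maintained for "Grades 1 and Grade 2 $\geq 1200". The next row, "Grade 2 < 1200 and Grade 3", carries the instruction "Hold sunitinib until ANC $\geq$ 1,000, then reduce 1 dose level and resume treatment". Grade 4 has its own row with the same instruction.

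**Fatigue, Section 3.3.1.** Grades 1 and 2 maintain the dose. The action row covers "Grade 3 (and severe Grade 2, at investigator discretion" and instructs "Hold sunitinib until $\leq$ Grade 2, then reduce 1 dose level and resume treatment".

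**Day-1 criteria, Section 3.3.** "Patients may continue to receive therapy provided the following criteria are met on day 1 of each cycle": the list includes an ANC of at least 1.0 × 10^9/L and "Non-hematological toxicity recovered to < grade 2 (or tolerable grade 2 or baseline". No dose level is attached to these criteria.

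**Scope of reductions.** Sections 3.2 and 3.3 describe reductions (to 37.5 mg, then 25 mg) for Grade 3 or 4 sunitinib-related toxicity. A later bullet in Section 3.3 also permits reduction under the table.

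**Grading, Section 3.1.2.** "Toxicities will be graded according to the Common Terminology Criteria for Adverse Events (CTCAE) Version 5.0". The numeric grade limits for ANC are not printed.

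**The concern.** A hold rule needs a release condition that is not yet met when the hold starts. In these two places it is already met, so the instruction to hold does nothing over part of its own trigger range.

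Staff then have to work out what was meant. One could follow the order of the words and reduce at once. Another could assume that a real interruption was intended. On day 1 of a cycle, a third could look only at the Section 3.3 criteria and continue without a change.

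The point at stake is whether a written safety rule is applied in the same way to patients with the same observation.

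**Working it through.** There is no sample size, power or error rate to reproduce. The check takes each row of the table and asks whether any observation both triggers the hold and meets its release condition.

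**Units.** The day-1 limit of 1.0 × 10^9/L equals 10^9 ÷ 10^6 = 1,000 per mcL, the same number as the table's release limit.

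**Neutropenia.** The trigger is ANC < 1,200 and the release is ANC ≥ 1,000. The two overlap from 1,000 to 1,199, which is 1,199 − 1,000 + 1 = 200 whole-number values.

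This does not depend on the unprinted grade limits. The table places values of 1,200 and above in Grade 2, so lower values cannot be Grade 1. The rows for Grades 2, 3 and 4 all release at 1,000. With the lower limit of Grade 2 taken as an assumption:

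| Assumed Grade 2 lower limit | Overlapping values in Grade 2 | Overlapping values in Grades 3–4 | Total |
|---|---|---|---|
| 500 | 200 | 0 | 200 |
| 750 | 200 | 0 | 200 |
| 1,000 | 200 | 0 | 200 |
| 1,100 | 100 | 100 | 200 |

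Below 1,000 there is no overlap, and the hold works.

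**Fatigue.** The trigger is Grade 3, or severe Grade 2 if the investigator chooses. The release is Grade 2 or lower. Severe Grade 2 always meets the release condition. Grade 3 never does, so its hold works.

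**Other rows.**

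| Row | Trigger | Release | Overlap |
|---|---|---|---|
| QTc | ≥ 550 msec | < 550 msec | none |
| AST/ALT | > 5 × ULN | ≤ 5 × ULN | none |
| Hand-foot syndrome | Grade 3 | ≤ Grade 1 | none |
| Thrombocytopenia | Grades 2–4 | platelets ≥ 75,000 | depends on the Grade 1 lower limit, which is not printed |

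For thrombocytopenia, an assumed Grade 1 lower limit of 50,000 or 75,000 gives no overlap. An assumed limit of 100,000 would give an overlap of 100,000 − 75,000 = 25,000. No finding is made on that row.

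**Table against day-1 rule.**

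| Observation on day 1 | Section 3.3.1 | Section 3.3 |
|---|---|---|
| ANC 1,000–1,199 | hold (already released), reduce one level, resume | may continue; no dose stated |
| Severe Grade 2 fatigue, row invoked | hold (already released), reduce one level, resume | continue only if the Grade 2 is tolerable or is the baseline level |

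The Study Calendar (Section 3.5) schedules blood counts on days 1 and 8 of cycle 1, then on day 1 of each later cycle, and at the end-of-treatment visit. From cycle 2, every scheduled on-treatment ANC is therefore a day-1 value to which both sections apply.

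**The case against.** The strongest reply is that the rows still lead to one action. Each says to hold until the limit is met, then reduce one level and resume. If the limit is already met, the patient is reduced and continues. Reduction alone at milder values, with a real hold only at worse ones, would be a coherent graded rule. This stands as a literal reading, and it means the table does not simply tell staff to stop and restart at the same dose. It does not show that an immediate reduction was intended: no text says so, and the word hold remains without effect.

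Second, a reader might infer a direct contradiction on ANC between Sections 3.3 and 3.3.1. The documents do not support that. Section 3.3 gives permission to continue and does not set the dose, and its next bullet refers dose reduction to the table. Continuing one level lower satisfies both. What remains is that the day-1 rule is silent on dose.

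Third, the fatigue trigger is discretionary, so some variation between investigators is accepted by design, and not every severe Grade 2 fatigue is affected. The day-1 tolerability test also gives a working check at the next cycle. Both points stand. However, the discretion concerns whether to invoke the row, not when the hold ends, and the day-1 test does not repair the rule within a cycle.

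Fourth, a reader might take the toxicity rates in Section 11.2.2 as evidence that these rules will be used often. They cannot serve that purpose. The 49.0% is fatigue of all grades, and the 13.5% is neutropenia of Grades 3 to 5. Neither measures the affected subset. Scheduled counts from cycle 2 also follow the rest week, so within-cycle ANC holds may be uncommon.

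**Conclusion.** This is an internal inconsistency in a safety rule. The hold is empty for ANC 1,000–1,199 (200 whole-number values) and for severe Grade 2 fatigue when the investigator invokes the row. The literal result is an immediate one-level reduction. The rest of the neutropenia and fatigue rows works as written.

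Two related points belong with it. The day-1 criteria in Section 3.3 state no dose action for the same ANC and use a different fatigue recovery test. The statements in Sections 3.2 and 3.3 that tie reductions to Grade 3 or 4 toxicity sit awkwardly with rows that reduce for Grade 2, although the later bullet in Section 3.3 allows reduction under the table.

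The ANC result assumes only that grades worsen as ANC falls and that the table's own grade labels are right. The fatigue result needs no assumption.

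A reader might go further and infer an effect on trial results, for example on the adverse-event rate listed as a secondary objective. The documents give no frequency for the affected observations, so no such effect can be sized, and none on the response-rate analysis or its stopping boundaries is claimed. The inconsistency should be corrected, but it does not undermine the design.

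**What to change.** Reconcile the trigger and release conditions for neutropenia and fatigue in Section 3.3.1 with each other, with the day-1 criteria in Section 3.3, and with the general statements on reductions in Sections 3.2 and 3.3. After the change, no observation should meet hold and release together, and the dose action on day 1 should be clear for each value. If an immediate reduction without a hold is what the rows are meant to give, the table should say so. The clinical team decides the thresholds; none is proposed here.

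The cost is a wording amendment to these sections. Sample size, error rates and analyses are unaffected.

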#### **Boxed Warning:**

Sunitinib has been associated with hepatotoxicity, which may result in liver failure or death. Liver failure has been observed in clinical trials (7/2281 [0.3%]) and post-marketing experience. Liver failure signs include jaundice, elevated transaminases and/or hyperbilirubinemia in conjunction with encephalopathy, coagulopathy, and/or renal failure. Monitor liver function tests (ALT, AST, bilirubin) before initiation of treatment, during each cycle of treatment, and as clinically indicated. Sunitinib should be interrupted for Grade 3 or 4 drug-related hepatic adverse events and discontinued if there is no resolution. Do not restart sunitinib if patients subsequently experience severe changes in liver function tests or have other signs and symptoms of liver failure. Safety in patients with ALT or AST  $>2.5 \times$  ULN or, if due to liver metastases,  $>5.0 \times$  ULN has not been established.

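### The AST/ALT row of table 3.3.1 permits restart after a second severe liver-test rise, which the boxed-warning text in 11.2.2 rules out if 'severe' means grade 3–4

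*Combined protocol and SAP*

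**What the plan says.** Two parts of the combined protocol and SAP deal with resuming sunitinib after liver toxicity.

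- **Section 3.3.1, AST and/or ALT elevation, grades 3 and 4.** Dosing is delayed if ALT or AST exceeds 5 × ULN and/or bilirubin exceeds 3 × ULN. Then: "Sunitinib may be re-administered when levels of ALT and AST are" no higher than 5 × ULN and bilirubin is no higher than 3 × ULN. One exclusion follows: "Sunitinib should not be re-administered if subjects develop" hepatic failure of grade 3 or worse by CTCAE version 5. The row says nothing about a repeat episode and does not point to 11.2.2.
- **Section 11.2.2, Boxed Warning.** For the event itself: "Sunitinib should be interrupted for Grade 3 or 4 drug-related hepatic adverse events and discontinued if there is no resolution". For what follows: "Do not restart sunitinib if patients subsequently experience severe changes in liver function tests or have other signs and symptoms of liver failure". The words 'severe' and 'subsequently' are not defined there.

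**The concern.** Section 3.3.1 is the text that a treating physician opens when a liver test comes back high. It sets a recovery threshold and one exclusion, and applies them identically however many episodes the patient has had. Section 11.2.2, in the drug-information part of the same protocol, makes a later severe liver-test change a reason not to restart, without waiting for hepatic failure of a given grade. A physician who follows the row alone could therefore re-expose a patient whom the protocol elsewhere says should not be re-exposed. Hepatotoxicity is the subject of the drug's boxed warning, and the protocol states that it can end in liver failure or death. What is at stake is the safety of individual patients.

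**Working it through.** No arithmetic applies. The check follows one patient through both texts and then asks whether any other rule closes the gap.

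**Assumptions.** 'Severe' is read as grade 3–4. The row itself pairs grades 3 and 4 with ALT or AST above 5 × ULN, so that threshold is used. The rises are judged drug-related, and hepatic failure does not develop.

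| Step | Row in 3.3.1 | Boxed-warning text in 11.2.2 |
|---|---|---|
| 1. ALT rises above 5 × ULN | Delay | Interrupt |
| 2. ALT settles within 4 weeks | Restart permitted | Restart not barred, since the event resolved |
| 3. After restart, ALT again exceeds 5 × ULN | Delay | A subsequent severe change has occurred |
| 4. ALT settles again within 4 weeks | Restart permitted | Do not restart |

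The texts agree up to step 3 and part at step 4. 'Subsequently' could mean after the interruption or after the restart. The row permits restart on either meaning, so this ambiguity does not remove the difference.

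**Other rules that might force a stop at step 4:**

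1. Section 3.3, delay limit: "If treatment is delayed for more than 4 weeks due to treatment associated toxicity, the patient will be discontinued from treatment". This caps the length of a delay. It does not count episodes, and the patient above never exceeds it.
2. Section 3.3, criteria for day 1 of each cycle: "Non-hematological toxicity recovered to < grade 2 (or tolerable grade 2 or baseline"). This affects when dosing may resume. Once the patient has recovered, it does not ask whether the rise was the first or the second.
3. Section 3.6.1, unacceptable toxicity: defined by reference to section 3.3, which has no rule on recurrent liver-test elevation.
4. Sections 3.6 and 3.6.1 (investigator discretion) and 7.4.1 (weekly team review): these allow a stop but do not require one.
5. Sections 7.3.1 and 7.3.3: a transaminase abnormality with raised bilirubin and no other known cause is reported to the company as a serious event within 24 hours. This adds oversight, not a stopping rule.

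None of these requires discontinuation. The only text that does is 11.2.2.

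**The case against.** The strongest reply is that the row grants a permission and 11.2.2 imposes a prohibition. Both belong to one protocol, and an investigator satisfies both by not restarting. That is right as far as it goes. A reader might infer that the protocol lacks the prohibition, or that it directs rechallenge. It does neither. What stands is that the operative dosing rule, used as written, allows what the other section forbids, with no cross-reference and no statement of which governs.

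The second reply concerns the word 'severe'. The boxed-warning sentence goes on to mention other evidence of liver failure, so one could hold that the severe changes it means are themselves part of liver failure. On that reading the row's exclusion covers much the same ground. What remains would be liver failure short of CTCAE grade 3, which cannot be judged because the documents do not reproduce that definition. This objection stands as a condition on the finding: the conflict is clear only if 'severe' means grade 3–4.

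Three stronger readings are tempting and fail:

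- **That a single grade 3–4 rise that resolves already sets the two texts against each other.** It does not; 11.2.2 calls for interruption, and for discontinuation only without resolution.
- **That the protocol lets dosing go on when the event does not resolve.** The row withholds drug until its limits are met, and section 3.3 ends treatment after more than 4 weeks of delay.
- **That the liver row is uniquely lax within the table.** The hand-foot syndrome row also leaves the restart dose to the physician.

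**Conclusion.** The point holds in a limited form. With 'severe' read as grade 3–4, the AST/ALT row allows a rechallenge after a second drug-related rise that recovers within 4 weeks. The boxed-warning text forbids it, and no other rule compels a stop. The reading of 'severe' is an assumption for the investigator to confirm.

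The number of patients affected cannot be derived, because the documents give no rate for a further severe rise after interruption. It is likely to be low, since it takes a first severe rise, recovery, restart, a second severe rise and a second recovery in time. A reader might infer a size from the one hepatic frequency the protocol gives: "Liver failure has been observed in clinical trials (7/2281 [0.3%]) and post-marketing experience". That figure counts liver failure, not restart after a recurrent rise, and hepatic failure of grade 3 or worse is already barred by the row. It should not be used as a measure here.

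The primary and secondary endpoints, the stopping boundaries and the sample size are unaffected. The change is still worth making, because the possible harm is serious and one edited row removes the inconsistency.

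**What to change.** Amend the restart text of the AST/ALT row so that sunitinib is permanently discontinued if either of these occurs:

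1. a grade 3–4 drug-related elevation of ALT, AST or bilirubin recurs or worsens after interruption; or
2. other evidence of liver failure appears, in the terms 11.2.2 already uses: "Liver failure signs include jaundice, elevated transaminases and/or hyperbilirubinemia in conjunction with encephalopathy, coagulopathy, and/or renal failure".

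Add a cross-reference from the row to the boxed-warning text in 11.2.2, and have the investigator confirm that 'severe' means grade 3–4. The row's existing exclusion for hepatic failure can stay.

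The cost is one edited table row by amendment. No new tests are needed, because the row already requires liver tests at baseline and during each cycle. The downside is that a few patients lose the option of rechallenge.
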